**CCDS:**

Morphological flow profile and PSV of CFA and A. poplitea

**4 ABI:**

Designation	ABI value
no PAD	>0.9-1.3
mild PAD	0.75-0.9
moderate PAD	0.5-0.75
severe PAD	<0.5
mediasclerosis	>1.3

**5 Clinical scores:**

Relative and absolute walking distance

Fontaine classification

I>No symptoms

IIa=painless walking distance >200 m, IIb=painless walking distance <200 m

III=pain while resting

IV=trophic disorder

Rutherford classification

0>No symptoms

1=mild claudication

2=moderate claudication

3=severe claudication

4=ischemic rest pain

5=minor tissue loss (nonhealing ulcer, focal gangrene and diffuse pedal ischemia)

6=major tissue loss (extending above transmetatarsal level, foot no longer salvageable)

**6 Determination of Sample Size**

Based on the data collected until 05.03.2021 the case number calculation (no interim analysis) was performed in cooperation with the Institute of Biometry. Six of a total of 102 persons included up to the above-mentioned date were diagnosed with PAD stage III according to Fontaine. In the course of the study, it became apparent that a sample size calculation based on 30 patients with stage III disease and 30 healthy subjects, as initially planned, could not be realised during a realistic time period.

In order to establish a valid case number as early as possible, the two critical PAD stages III and IV were formally combined into one group to be considered together as chronic critical limb ischemia. Thus, based on the results of a total of 33 healthy study subjects and 29 subjects diagnosed with a critical PAD stage, the exemplary case number calculation could be accomplished. A power analysis, which allowed a power of 80% at an alpha of 0.05 (unilateral) was performed to determine the final sample size. For the MSOT parameter deoxygenated hemoglobin, the number of subjects was approximately 33, and for the MSOT parameter oxygenated hemoglobin, the number of subjects was approximately 11 for each of the individual groups (healthy control group, PAD stage II, PAD stage III-IV).

Dropout is not considered because the study is performed during a single visit.

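### The sample size was fixed from group results of 62 of the trial's own subjects, so the stated 80% power does not describe a study group 1 test that includes them

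*SAP*

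**What the plan says.** SAP section 6 and protocol 8.2 give the same account. By the data cut of 05.03.2021, "Six of a total of 102 persons included up to the above-mentioned date were diagnosed with PAD stage III". The basis originally intended, "a sample size calculation based on 30 patients with stage III disease and 30 healthy subjects, as initially planned", was judged unrealistic, so stages III and IV were merged. The calculation was then made "based on the results of a total of 33 healthy study subjects and 29 subjects diagnosed with a critical PAD stage". The step is described thus: "the case number calculation (no interim analysis) was performed in cooperation with the Institute of Biometry".

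Its purpose is explicit: "A power analysis, which allowed a power of 80% at an alpha of 0.05 (unilateral) was performed to determine the final sample size". The result: "For the MSOT parameter deoxygenated hemoglobin, the number of subjects was approximately 33", and about 11 for oxygenated Hb, in each of three groups (healthy, stage II, stage III-IV).

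Neither document states the effect size, the SD, a re-sizing rule, a cap or an adjustment of alpha.

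Four other places bear on the point:

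- Protocol 7.2 runs the two study groups in series, group 1 first.
- SAP 7.2 covers all eligible enrolled subjects and does not exclude the 62.
- SAP 9 makes a significant group difference the gate to ROC analysis.
- SAP 9.2 specifies ANOVA with Tukey comparisons of three pairs at 95% family-wise confidence.

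**The concern.** Outcome results labelled by group were used part-way through to settle the final number, and the same paragraph says that no interim analysis took place. A reader would take 80% power and a one-sided 5% level as properties fixed before the data were seen.

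The requirement of 33 per group for Hb almost equals the 33 and 29 already measured. If those subjects stay in the group 1 test, most of that test's outcome was known when its power was stated.

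This matters because the test decides which readouts go on to ROC analysis. The cutpoint in SAP 9.3 also comes from the same contrast, controls against stages III/IV.

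**Working it through.** **Inputs.** From SAP 6: power 80%, alpha 0.05 one-sided, n about 33 (Hb) and 11 (HbO2) per group, data from 33 healthy and 29 stage III/IV subjects. From SAP 9.2: Tukey, three pairs, 95% family-wise. From SAP 5.2: about 200 subjects in five similar groups, so about 200/5 = 40 each. SAP 5.2 does not say how the 200 divide between study groups 1 and 2.

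**Step 1: the plan's own figure.** Without an effect size and SD, 33 and 11 cannot be reproduced forward. They can be solved backwards for the standardised difference d.

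- Normal approximation: n = 2(1.645 + 0.842)²/d². With n = 33, d = 0.612; with n = 11, d = 1.060.
- Noncentral t: d = 0.619 and 1.098.

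The t-based values are used below. The normal ones lead to the same conclusions.

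**Step 2: what was already in hand.** Assume that these d are the observed effects. At 33 against 29, t = d × √(33 × 29/62) = d × 3.929.

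- Hb: 0.619 × 3.929 = 2.43, one-sided p = 0.009.
- HbO2: 1.098 × 3.929 = 4.31, one-sided p = 0.00003.

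**Step 3: what 80% means for a test that includes these subjects.** Reaching 33/33 for Hb takes four more critical-stage patients. Suppose those four show on average no difference from controls. The pooled difference becomes 29 × 0.619/33 = 0.544 SD, and z = 0.544/√(2/33) = 0.544/0.246 = 2.21, still above 1.645. Allowing for sampling variation in the four, the one-sided test rejects with probability about 0.99 even if the true effect is zero. It rejects with probability above 0.999 if the true effect equals the observed one. Neither figure is 80%.

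**Step 4: a fresh sample of 33 per group (Hb).** SE(d) = √(62/(33 × 29) + 0.619²/(2 × 62)) = 0.26. The 95% CI is 0.619 ± 1.96 × 0.26, or 0.11 to 1.13. Power of the one-sided 5% t-test is 11% at the lower end and 99.8% at the upper. Averaged over a normal distribution with mean 0.62 and SD 0.26, it is about 72%.

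**Step 5: the test actually planned.** With three groups of 33, the Tukey critical value is q(0.95; 3, 96)/√2 = 2.381. The standardised difference is 0.619/0.246 = 2.513. Power for the pair is Φ(2.513 − 2.381) = Φ(0.13), about 55%.

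**Step 6: type I error.** No re-sizing rule is documented, so a range is needed. At nominal one-sided 5%, with the 62 reused and no adjustment:

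| Assumed rule | Type I error |
|---|---|
| Only the SD taken from the data | 5.0% |
| Effect-driven, continue to a cap of about 40 per group | 5.1% |
| Effect-driven, cap at twice the current size | 5.6-5.7% |
| Effect-driven, cap at three times the current size | 5.9-6.3% |
| Effect-driven, no cap | 6.2-8.7% |
| Effect-driven, study abandoned if n exceeds a cap of about 40 | 1.35% |
| Effect-driven, study abandoned if n exceeds three times the current size | 3.2-3.6% |

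**The case against.** The strongest defence has four parts.

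1. **The text says only that results were used.** If the data supplied just the SD, the level stays at 5.0%. This is possible but unlikely. An SD-only calculation needs a target difference and none appears, while two parameters on the same subjects gave 33 and 11. Use of the observed effects remains a strong inference, not a stated fact.
2. **Retention of the 62 in the group 1 test is implied, not stated.** It follows from the serial design and from the absence of any exclusion. That is why the conclusion is conditional and the fix asks for a statement.
3. **The study is described as explorative and the calculation as exemplary.** The primary endpoint is a threshold, and study group 2 checks the cutpoint. This limits the damage: validation is unaffected if the group 2 subjects are new. It does not make the stated 80% correct.
4. **Sizing from in-study data was intended from the start and is openly described.** This stands. A reader might infer a concealed look at the data, and the documents do not support that. The fault is the label and the missing detail.

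A reader might also infer that the group 1 type I error is known to exceed 5%. The documents do not support that either. The level depends on a rule that they do not give, it can fall below 5%, and at about 40 per group the excess is about 0.1 percentage point. One-sided 5% is in any case not the level of the ANOVA/Tukey test.

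**Conclusion.** The point holds for power. Provided that the observed effects were used and the 62 subjects remain in study group 1, the 80% does not describe the group 1 test, because the Hb and HbO2 contrasts were already significant when the number was set. Even for entirely new subjects the figure is conditional on an imprecise estimate.

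The Tukey shortfall does not depend on data reuse. It assumes a true effect of 0.62, three equal groups of 33 and a common SD.

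For the error level, the supportable statement is only that the nominal 5% is not guaranteed.

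Nor should 80% be transferred to study group 2. No size is stated for that group, and an average of about 72% applies even if it has 33 per group.

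**What to change.** **SAP 6 and protocol 8.2.** Replace the remark that there was no interim analysis with a statement that the sample size was re-estimated using group results of enrolled subjects. Give the effect, the SD and the rule used, and say whether the 62 subjects stay in study group 1. Restate 80% as conditional on the observed effect for a one-sided two-group test. Add the range and average for a fresh sample and the lower figure for the planned Tukey comparison. Make no 80% claim for study group 2 unless its size is stated.

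**SAP 9.2.** Keep the group 1 tests as the gate to ROC analysis, since SAP 9 needs them there, but label their p-values exploratory. Rest confirmatory statements on the validation of the cutpoint in study group 2.

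**Cost.** Wording changes in both documents and a less favourable stated power. No extra patients.

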**8.2 Participant number**

A previous performed valid case number calculation based on the results of the pilot study was not possible due to the small number of patients and cohort studied (PAD IIb, healthy leg versus affected leg).

Based on the data collected until 05.03.2021 the case number calculation (no interim analysis) was performed in cooperation with the Institute of Biometry. Six of a total of 102 persons included up to the above-mentioned date were diagnosed with PAD stage III according to Fontaine. In the course of the study, it became apparent that a sample size calculation based on 30 patients with stage III disease and 30 healthy subjects, as initially planned, could not be realized during a realistic time period.

In order to establish a valid case number as early as possible, the two critical PAD stages III and IV were formally combined into one group to be considered together as chronic critical limb ischemia. Thus, based on the results of a total of 33 healthy study subjects and 29 subjects diagnosed with a critical PAD stage, the exemplary case number calculation could be accomplished. A power analysis, which allowed a power of 80% at an alpha of 0.05 (unilateral) was performed to determine the final sample size. For the MSOT parameter deoxygenated hemoglobin, the number of subjects was approximately 33, and for the MSOT parameter oxygenated hemoglobin, the number of subjects was approximately 11 for each of the individual groups (healthy control group, PAD stage II, PAD stage III-IV).

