## 7 General Considerations

### 7.1 Timing of Analysis

The final analysis will be performed after the last patient entered into the study. Study collectives for study group 1 (derivation of thresholds) and study group 2 (validation of thresholds) will be handled separately.

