## 9 Diagnostic Performance Analysis

Diagnostic performance will be examined in different successive steps: first, distribution of single MSOT readouts within the different PAD stages used as external criterion (gold standard) will be assessed. Second, the difference in means of the (MSOT) readouts between patient subgroups will be assessed and statistically tested. If significant, these readouts will be subject to a ROC analysis to determine the optimum cutpoint; further details see below.

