## 9.2 Differences in Severity of PAD

Overall differences of MSOT readouts vs. the PAD stages will be statistically tested using ANOVA including a post hoc Tukey test, comparing all three pairs deriving a 95% family-wise confidence level of differences between means.

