## 9.3 Sensitivity and Specificity

Using the cutpoint maximising the Youden index derived from study group 1 based on controls vs. PAD classes III/IV, the diagnostic properties of MSOT values will be illustrated by sensitivity and specificity (with 95% CI) associated with a diagnostic test decision dichotomised at that cutpoint. The same cutpoint will be employed in study group 2 for validation of diagnostic properties.

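### The stated 80% power (one-sided 0.05, from healthy vs stage III-IV data) does not describe the planned three-group ANOVA/Tukey analysis, and the size of the gap depends on inputs that are not given

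*SAP*

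**What the plan says.** SAP section 6 and Protocol 8.2 give the same calculation. Its basis is "based on the results of a total of 33 healthy study subjects and 29 subjects diagnosed with a critical PAD stage", and its operating point is "A power analysis, which allowed a power of 80% at an alpha of 0.05 (unilateral) was performed to determine the final sample size". The result is about 33 subjects for Hb and, for HbO2, "approximately 11 for each of the individual groups (healthy control group, PAD stage II, PAD stage III-IV". Neither document gives the test, the mean difference, the SD or any stage II data used. The SAP also describes the exercise in softer terms: "the exemplary case number calculation could be accomplished".

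SAP 9.2 tests differences between PAD stages "using ANOVA including a post hoc Tukey test, comparing all three pairs deriving a 95% family-wise confidence level". SAP 9 then uses the result as a filter: "If significant, these readouts will be subject to a ROC analysis to determine the optimum cutpoint". SAP 9.3 derives the cutpoint from one contrast: "Using the cutpoint maximising the Youden index derived from study group 1 based on controls vs. PAD classes III/IV". On the two study groups, SAP 7.1 says: "Study collectives for study group 1 (derivation of thresholds) and study group 2 (validation of thresholds) will be handled separately".

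**The concern.** The power statement and the analysis differ in three ways.

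- **Direction.** The calculation is one-sided. The F test and Tukey intervals are non-directional by construction, and the null hypotheses in SAP 4.1 name no direction. The SAP does not itself write that the tests are two-sided.
- **Multiplicity.** The calculation states alpha 0.05 and mentions no adjustment. SAP 9.2 controls the error over three pairs.
- **Groups.** The data come from healthy and stage III-IV subjects only, but the n is assigned to stage II as well.

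What is at stake is interpretation. Only significant readouts go on to ROC analysis, so the absence of an Hb cutpoint could reflect low power rather than no signal. A null Hb result or a null stage II contrast could likewise be read as coming from an 80%-powered test.

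**Working it through.** **The plan's own figures.** The 33 and 11 cannot be reproduced, because the test, difference and SD are missing. The check therefore runs backwards: assume a test, solve for the standardised difference d that gives 80% power at the stated n, and carry that d into the planned analysis. Feeding d back returns 33 and 11, but that is circular and confirms nothing.

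**Inputs from the documents.** Power 80%; alpha 0.05 one-sided; n = 33 (Hb) and 11 (HbO2) per group; three groups; Tukey at 95% family-wise.

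**Assumptions.** Equal group sizes; a two-sample t-test behind the calculation; the three pairs are those among healthy, II and III-IV. SAP 9.2 speaks of PAD stages but does not name the groups, and the aTASC scheme in SAP 5.4 also has three categories.

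**Step 1, implied effect.** Power = P[T(df = 2n−2, δ) > t(1−α)], where T is noncentral t and δ = d√(n/2).

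- Alpha 0.05, n = 33: critical t 1.669, δ = 2.513, d = 2.513/√16.5 = 0.619.
- Alpha 0.05, n = 11: d = 1.098.
- Alpha 0.05/3, n = 33: d = 0.744. For n = 11: d = 1.344.

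**Step 2, Tukey pair, healthy vs III-IV.** The critical value is q(0.95; 3, df)/√2 with df = 3(n−1). At 33 per group df = 96 and the critical value is 2.381. For Hb in the unadjusted case δ stays at 2.513 while the threshold rises from 1.669 to 2.381, so power falls from 80% to 55%.

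**Step 3, overall F.** λ = nΣ(μᵢ−μ̄)². With stage II midway, λ = 33d²/2. With stage II equal to one of the other groups, λ = 33 × (2/3)d². The critical F(2, 96) is 3.09. For d = 0.619, λ = 6.32 or 8.42.

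Results at 33 per group:

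| Parameter and assumed origin of n | d | Tukey pair, healthy vs III-IV | Overall F (II midway / at an end) |
|---|---|---|---|
| Hb, one-sided 0.05 | 0.619 | 55% | 59% / 73% |
| Hb, one-sided 0.05/3 | 0.744 | 74% | 76% / 88% |
| HbO2, one-sided 0.05 | 1.098 | 98% | at least 98% |
| HbO2, one-sided 0.05/3 | 1.344 | above 99% | above 99% |

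At 11 per group the HbO2 Tukey pair has 55% or 75%.

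**Step 4, break-even.** Solving the Tukey power for 80% at 33 per group gives d = 0.795.

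**Step 5, stage II.** If stage II has half the III-IV effect (an assumption, since no stage II data are cited), the stage II vs healthy Tukey pair at 33 per group has 14-20% power for Hb and 44-64% for HbO2.

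**The case against.** **The calculation is called exemplary and uses the contrast that sets the cutpoint.** Both are true, and they limit the impact. The SAP nevertheless says that the power analysis was done to fix the final sample size, and the 80% carries no qualification.

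**The inputs are unknown, so a loss of power is not proven.** This stands as a limit on size. If alpha had been split six ways, n = 33 would imply d = 0.815 and the Tukey pair would have 82%. Nothing in the documents suggests such a split, but nothing excludes it. A reader might infer that Hb power is simply 55%. The documents do not support a single figure.

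**The gate may be the overall F.** SAP 9 does not say which test decides. If it is the F test and alpha was already adjusted, Hb has 76-88%, which may be adequate.

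**The sample is too small for two study groups.** A reader might infer this from SAP 5.2: five similar groups out of about 200 give 200/5 = 40 controls, against 2 × 33 = 66. That holds only if 33 is per study group, which is not stated. Equally, 3 × 33 × 2 = 198 is close to the anticipated 200, although the documents do not make that link. SAP 5.2 describes its figures as current expectations, so no firm conflict can be claimed.

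**Conclusion.** The mismatch is certain from the text: the 80% is stated for a one-sided 0.05 calculation on healthy and III-IV data, and the planned analysis is a family-wise, non-directional comparison of three groups. Its size is conditional on the assumed origin of n and on the reading of the three pairs. On the two readings worked through, the Hb pair has 55% or 74% at 33 per group, and 80% requires d of about 0.80 or more.

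Two stronger conclusions are tempting and do not follow. The figures 33 and 11 are not shown to be arithmetically wrong; they cannot be checked. Nor is the primary endpoint blocked: on the effects implied by n = 11, HbO2 would very probably pass the significance step at 33 per group. The practical risk is confined to over-reading a null Hb result or a null stage II contrast. This should be fixed, mainly as a matter of correct statement.

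**What to change.** 1. In SAP 6 and Protocol 8.2, limit the claim. Suggested wording: *The 80% power refers to a one-sided comparison (alpha 0.05) of healthy controls with PAD III-IV by [test], with effect size [ ] and SD [ ] for Hb, and [ ] and [ ] for HbO2. Comparisons involving PAD II were not powered.* If stage II data were used, give them in place of the last sentence.
2. From those inputs, report the power of the SAP 9.2 ANOVA/Tukey analysis at the planned group sizes, replacing the unqualified 80%.

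Minor clarifications: name the three groups in SAP 9.2; say in SAP 9 whether significance means the overall F or the controls vs III/IV pair; say in SAP 6 whether 33 is per study group and, if so, reconcile it with SAP 5.2. If the pooling of III and IV is described at the same time, it should not be said to serve only the sample size and the three-pair analysis, because SAP 9.3 also uses it to derive the cutpoint.

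The cost is wording and one power calculation from inputs the sponsor should already hold. There are no extra patients and no change of analysis. The reported power for Hb will probably look less favourable.

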## 7 General Considerations

### 7.1 Timing of Analysis

The final analysis will be performed after the last patient entered into the study. Study collectives for study group 1 (derivation of thresholds) and study group 2 (validation of thresholds) will be handled separately.

### 7.2 Analysis Population

We will describe all screened and enrolled subjects who fulfil all inclusion criteria and fail all exclusion criteria.

### 7.3 Subgroups

Subpopulations are defined the reference standard as follows: clinical according to Fontaine and TASC classification (and if necessary and in order to confirm a flow relevant stenosis CCDS).

### 7.4 Missing Data

For the primary endpoint, single missing values will have no consequence. If missing, the individual subject will be excluded for the specific sub-analysis.

[figure not shown]
## 8 Summary of Study Data

Information on continuous variables will be given as means and standard deviations.

Categorical variables will be summarized as frequencies or percentages of observed levels.

### 8.1 Subject Disposition

Flow of study subjects.

## 8.2 Protocol Deviations

Protocol deviations that influence the analysis and consequences:

- Not fulfilling inclusion criteria ○ Subjects will not be included in the full analysis population
- Withdrawal of consent ○ Subjects will not be included in the full analysis population
- Withdrawal of consent to read medical file ○ Subjects will not be included in the full analysis population
- Drop-out for other reasons ○ Subjects will not be included in the full analysis population
- Single missing values ○ Subjects will be included in the full analysis population

## 8.3 Clinical Investigation Plan Deviations

Data will be analyzed according to the Statistical Analysis Plan; any further/additional/deviation from the Statistical Analysis Plan will be reported as such.

## 8.4 Baseline Variables

- Age
- Gender
- Affected leg/examined leg
- Risk factors for PAD (Smoking, arterial hypertension, lipid abnormalities, diabetes mellitus, obesity, positive family history)
- Relevant underlying diseases (CHD, CHF, atrial fibrillation, CKD, carotid artery stenosis, previous cerebrovascular event)
- Previous surgery or interventions on the arterial vessels of the lower extremity
- Current medication
- Date of last angiography

## 9 Diagnostic Performance Analysis

Diagnostic performance will be examined in different successive steps: first, distribution of single MSOT readouts within the different PAD stages used as external criterion (gold standard) will be assessed. Second, the difference in means of the (MSOT) readouts between patient subgroups will be assessed and statistically tested. If significant, these readouts will be subject to a ROC analysis to determine the optimum cutpoint; further details see below.

